### **10.3. Efficacy Evaluations**

A secondary objective of the study is to document any antitumor activity. Refer to [Attachment 1](#) for details regarding the timing of specific efficacy measures. Efficacy measures include:

- ORR: The proportion of patients who exhibit a confirmed complete response (CR) or PR relative to baseline as defined by RECIST 1.1 (Eisenhauer et al. 2009)
- DCR: The proportion of patients in the analysis population who exhibit a SD or confirmed CR or PR relative to baseline during the study
- PFS: The time from the date of study enrollment to the date of first observation of objective progression or death from any cause
- Change in tumor size: The change in tumor size from baseline measurement to the measurement with the smallest tumor size during the study.

Each patient will be assessed by one or more of the following radiologic tests for tumor measurement:

- CT scan
- MRI
- Chest x-ray.

Each patient's full extent of disease will also be assessed with:

- Tumor measurement by RECIST 1.1 (Eisenhauer et al. 2009)
- Evaluation of tumor markers, if indicated
- Evaluation of ECOG performance status (refer to [Attachment 6](#)).

Consistent with RECIST, all patients may undergo alternative imaging studies consistent with institutional guidelines to assess tumor response. This may include, but is not limited to, FDG-PET, dynamic contrasted-enhanced MRI, or other modalities.

To confirm objective responses, all lesions should be radiologically assessed, and the same radiologic method used for the initial response determination should be repeated at least 4 weeks following the initial observation of an objective response, using the sample method that was used at baseline. If a patient is discontinued from the study, repeat radiology assessments may be omitted if clear clinical signs of progressive disease are present.

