6.12. Efficacy Analyses

As a coprimary objective for Part B, this study will evaluate preliminary antitumor activity observed with ramucirumab in combination with LY2875358 in the tumor-specific expansion cohorts.

Overall Response Rate (ORR): ORR is defined as the proportion of patients who exhibit a confirmed CR or PR relative to baseline as defined by RECIST 1.1 (Eisenhauer et al. 2009).

ORR is computed as the number of responders divided by the total number of treated patients. A responder is defined as any patient who exhibits a confirmed CR or PR relative to baseline

assessment, done on or up to 7 days prior to Cycle 1 Day 1. Patients with response that is deemed not evaluable will be considered non-responders and will be included in the denominator for the purpose of calculating ORR. ORR will be assessed within each cohort, ORR with 95% CIs will be estimated using the Clopper-Pearson method.

Progression-Free Survival (PFS): The PFS time is measured from the date of receiving the first dose of study drug to the date of first objective progression as assessed by the investigator or the date of death due to any cause, whichever is earlier. Table 6.2 provides additional details. The censoring is taken in the following order:

- If a patient does not have a complete baseline disease assessment, then the PFS time will be censored at the enrollment date, regardless of whether or not objectively determined disease progression or death has been observed for the patient; otherwise,
- If a patient is not known to have died or have objective progression as of the data inclusion cutoff date for the analysis, the PFS time will be censored at the last evaluable objective progression-free disease assessment date.

If a patient has a missed visit prior to an event (progression or death), then the PFS time will be censored at the last evaluable assessment prior to the event.

Table 6.2. Definition of PFS

Situation	Outcome	Date of Progression or Censoring
Death before first objective PD assessment	Progressed	Date of death
Objective PD	Progressed	Date of first radiologic assessment showing progressive disease
No evaluable baseline tumor assessments	Censored	Enrollment date
No progression	Censored	Date of last radiologic assessment of measured lesions showing no progression
New systemic anticancer treatment started	Censored	Date of last radiologic assessment of measured lesions showing no progression prior to the commencement of new systemic anticancer treatment

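### SAP 6.12 censors PFS at enrolment when the baseline assessment is incomplete, even for a documented death; few patients should be affected, but one could carry a 15-patient cohort across its landmark

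*SAP*

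**What the plan says.** The PFS definition in SAP 6.12 starts at first dose and ends at objective progression or the "date of death due to any cause, whichever is earlier". Protocol 10.3 defines it as "The time from the date of study enrollment to the date of first observation of objective progression or death from any cause". Neither definition makes an exception for a missing baseline.

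The SAP then ranks its censoring rules: "The censoring is taken in the following order". The first reads "If a patient does not have a complete baseline disease assessment, then the PFS time will be censored at the enrollment date", and it applies "regardless of whether or not objectively determined disease progression or death has been observed for the patient". Table 6.2 repeats it: a patient with no evaluable baseline tumour assessment is censored at enrolment, with no exception for death. A separate row, "Death before first objective PD assessment", is an event on the date of death.

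Both documents define an enrolled patient as one who has received at least one dose (Protocol section 4; SAP Table JTBF.6.1). SAP 6.6 puts every treated patient in the efficacy population.

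Protocol 8.1.1 and SAP 5.2 allow disease control at a landmark as an alternative to response rate when deciding whether to take a cohort from about 15 to about 45 patients. Protocol Table JTBF.2 gives the PFS landmarks of interest: 60% for gastric/GEJ, and 75% for HCC, RCC and NSCLC. SAP Table JTBF.5.3 lists the same values as secondary critical success factors.

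**The concern.** Without a baseline scan, progression may be impossible to judge, so censoring for progression is reasonable. A death needs no baseline to be established, and both PFS definitions count it. Censoring at enrolment is censoring at about time zero. Under Kaplan-Meier, the patient leaves the risk set before the first event time and has no influence on the curve, although SAP 6.6 says that patient belongs to the efficacy population.

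What is at stake is the landmark PFS figure seen when expansion is discussed. With about 15 patients, one patient fewer in the denominator is worth several percentage points. Where the missing patient is a death before the landmark, the shift is upward.

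**Working it through.** **The plan's own figures.** The documents give no error rates for the landmark PFS criterion. Their figures at the 15-patient stage concern response: 1 − 0.90^15 = 79.4% (stated 79%) and 1 − 0.97^15 = 36.7% (stated 36.7%). Both reproduce, and the PFS rule does not affect either.

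**Inputs.** n = 15 per cohort (Protocol 8.1.1). Landmark of interest 60% (gastric/GEJ) or 75% (the other three), against previously observed 40% and 50% (Protocol Table JTBF.2).

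**Assumptions, because the documents are silent.** k patients lack a complete baseline and die before the landmark, with k = 1 to 3. Landmark PFS is estimated by Kaplan-Meier or by exclusion. No one else is censored before the landmark. The landmark is met if the estimate is at or above the value of interest.

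**Effect of censoring at time zero.** Take 15 patients with 11 progression-free past 4 months, three progressions at months 1, 2 and 3, and one death at month 1.5 in a patient without a baseline.
- Death counted: 14/15 × 13/14 × 12/13 × 11/12 = 11/15 = 73.3%.
- Death censored at enrolment: 13/14 × 12/13 × 11/12 = 11/14 = 78.6%.

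The denominator therefore falls from 15 to 15 − k.

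**Progression-free patients needed.**
- 75% landmark: 0.75 × 15 = 11.25, so 12 of 15. With one death censored, 0.75 × 14 = 10.5, so 11 of 14. One affected patient can reverse the comparison.
- 60% landmark: 0.60 × 15 = 9, so 9 of 15. With one death censored, 0.60 × 14 = 8.4, so still 9. With two, 0.60 × 13 = 7.8, so 8 of 13: 8/15 = 53.3% becomes 8/13 = 61.5%. Gastric needs two affected patients.

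**Chance of meeting the landmark when the other 15 − k patients have the previously observed PFS rate** (exact binomial tails; for example, k = 1 at the 75% landmark compares P(X ≥ 12) with P(X ≥ 11) for n = 14, p = 0.5):

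| k | 75% landmark, deaths counted | 75% landmark, SAP rule | 60% landmark, deaths counted | 60% landmark, SAP rule |
|---|---|---|---|---|
| 0 | 1.8% | 1.8% | 9.5% | 9.5% |
| 1 | 0.65% | 2.87% | 5.83% | 5.83% |
| 2 | 0.17% | 4.61% | 3.21% | 9.77% |
| 3 | 0.02% | 7.30% | 1.53% | 5.73% |

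These chances are conditional on k. They say nothing about how often such patients occur.

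**The case against.** **Rarity.** Measurable disease is an entry criterion (Protocol 7.1), a baseline scan is required within 28 days before treatment (Protocol Attachment 1), eligibility is checked with the sponsor before each enrolment (Protocol 9.3), and waivers are not permitted (Protocol 7). This stands: few patients should be affected, and k = 1 to 3 is an assumption. It does not bring the number to zero. SAP 6.3 itself provides for treated patients without measurable disease at baseline, and Protocol 8.2.1 lets inadvertently enrolled patients stay on study by agreement.

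**Discretion.** Expansion on the landmark may be considered if judged appropriate; it is not automatic. ORR is the co-primary endpoint, and deaths are listed individually under SAP 6.11.3, so decision-makers can see them. This also stands. The landmark figure may still be misreported.

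**Estimator.** The SAP text names none; Kaplan-Meier appears only through its reference list. A crude proportion over all 15 that counted these patients as failures would remove the inflation. This stands as a condition on the arithmetic.

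**Direction.** The rule drops patients without a baseline whether they die or survive. Its net effect is upward only if they do worse than the rest, which is plausible but not shown.

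A reader might also infer more than the documents support:
- *That Table 6.2 contradicts itself.* A patient without a baseline who dies early fits two rows, but the ranked order in the text resolves this in favour of censoring.
- *That SAP 6.3 conflicts with the rule.* Its treatment of non-evaluable patients is limited to ORR. The contrast is real, but a different convention for another endpoint is not a contradiction.
- *That early deaths in general are lost.* Deaths of patients with a baseline remain events, subject to the separate missed-visit rule.
- *That many patients will be caught because the SAP requires a baseline "done on or up to 7 days prior to Cycle 1 Day 1".* Those words belong to the ORR responder definition; nothing applies them to PFS. They do disagree with the protocol's 28-day scan window, which is a separate matter to correct.

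**Conclusion.** The rule as written gives a wrong result for a narrow group: treated patients without a complete baseline who are known to have died. For them it overrides the PFS definition of both documents.

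The effect on a 15-patient cohort is 78.6 − 73.3, about 5 points, for one such death in the example above, enough to cross 75% in HCC, RCC or NSCLC. In gastric it is 61.5 − 53.3, about 8 points, for two such deaths, enough to cross 60%. Both depend on the deaths falling before the landmark and on estimation by Kaplan-Meier or exclusion.

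This is a minor point, because such patients should be few and the landmark route is discretionary. ORR and the Simon response counts are unaffected by this rule. It is worth correcting because the change is small and the landmark analysis is otherwise under-specified.

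**What to change.** In SAP 6.12 and Table 6.2:
- Count a documented death as a PFS event on its date whatever the baseline status, subject to the separate missed-visit rule.
- Censor at first dose only when there is no evaluable baseline and no known death.
- Use one trigger in both places. The text says *complete* and the table says *no evaluable*; the text is the wider of the two and is not defined.
- State the estimator and denominator for landmark PFS.

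Separately, replace the 7-day baseline window in the ORR responder definition with the protocol's 28-day scan window.

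The core correction costs one sentence and one table row; the estimator and the ORR window are short additions. There are two drawbacks. PFS may look slightly less favourable. Patients without a baseline could then add events but no progression-free time, which pulls the estimate down. A sensitivity analysis under the current rule would show whether either matters.

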## Screening/Baseline Assessments

Relative Day Prior to Day 1 of Cycle 1	≤28	≤14	≤7	Comments
Informed Consent	X			Informed consent MUST be signed before performing any protocol procedure
Radiological Tumor Assessment (including head-contrasted CT or brain MRI)	X			These scans can be performed locally and may be from prior to consent if taken within 28 days of Day 1, Cycle 1. PET/CT allowed if CT portion is of diagnostic quality
Chest X-Ray	X			May be omitted in patients having a chest CT for their radiological tumor assessment
Functional Tumor Imaging	X			FDG-PET mandatory in Part B1 (gastric). Further functional tumor imaging (including but not limited to DCE-MRI, FLT-PET) is permitted in all patients if appropriate for the respective tumor type at the discretion of the investigator and considered institutional standard of care or is part of an appropriate imaging study open at the site.
Hepatitis B and C Screening	X			Screening is required (see Attachment 2 ); may be from prior to consent if done within 6 months of Day 1, Cycle 1; Hepatitis B surface antigen and hepatitis C (antibodies or RNA according to local standard)
“Post-Progression Tumor Sample” (baseline)	X			Mandatory (see Section 10.2.1 ); may be from prior to consent if taken within 8 weeks of Day 1, Cycle 1. If this is not available, patient must undergo a tumor biopsy pre-study treatment
Archival Tumor Sample	X			Optional (see Section 10.2.2 )
Medical History		X		Including alcohol/tobacco use/other relevant habits
Physical Examination		X		Including height and body weight
Vital Signs		X		Temperature, blood pressure (seated), heart rate, and respiration rate
Performance Status		X		Per ECOG scale (see Attachment 6 )
CTCAE Version 4.03 Grading (Preexisting Conditions)		X		To be reported only after study eligibility is confirmed. Refer to Section 10.1.2 for reporting expectations.
Concomitant Medications		X		See Section 9.5
Local 12-Lead Electrocardiogram		X		Single ECG
Hematology		X		See Attachment 2
Serum Chemistry including calculated creatinine clearance		X		See Attachment 2
Coagulation		X		See Attachment 2
Urinalysis		X		See Attachment 2
Immunogenicity		X		
Sampling for Exploratory Blood Biomarkers		X		See Section 10.2.2

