Radiological Tumor Assessment g	X										Every 6 weeks after initiation of study treatment; after Cycle 9 every 2-4 cycles as clinically indicated	
Functional Tumor Imaging	X h										FDG-PET mandatory in Part B1 (gastric) 6 weeks after initiation of study therapy	

Abbreviations: CNS = central nervous system; CT = computed tomography; CTCAE = Common Terminology Criteria for Adverse Events; DCE-MRI = dynamic contrasted-enhanced magnetic resonance imaging; ECG = electrocardiogram; ECOG = Eastern Cooperative Oncology Group; FDG-PET = 2-deoxy-2[F-18]fluoro-D-glucose positron emission tomography; FLT-PET = 3-deoxy-3[F-18]fluorothymidine positron emission tomography; fT4 = free thyroxine; PD = pharmacodynamics; PET = positron emission tomography; PK = pharmacokinetics; TSH = thyroid-stimulating hormone; V = visit.

a Short-term follow-up begins on the day after the patient's last dose of study drug and ends approximately 30 days later. This visit should be scheduled  $30 \pm 3$  days after last dose of study drug.

b Electrocardiograms must be recorded before any study drug is administered. In Cycle 1, Day 1 and 15 only, additional ECGs must be recorded pre- and post-LY2875358 infusion, immediately before collecting the corresponding PK samples.

- c Local hematology, coagulation tests, and urinalysis may be done within 2 days prior to administration of study drugs (except Cycle 1, Day 1 [within 3 days]). An additional local chemistry panel according to local standard of care may be done and used for on-study dosing decisions; if done so, chemistry testing must also still be performed by the central laboratory at the regularly scheduled time points. The central chemistry laboratory results will be used for patient eligibility and subsequent safety analyses. In exceptional cases, patient may be enrolled based on local chemistry results after discussion with the sponsor if central laboratory samples results required for eligibility are not available in a timely manner (e.g., due to inclement weather conditions).
- d If, while receiving the investigational product(s), a patient has proteinuria  $\geq 2+$  per a dipstick or routine urinalysis test, a 24-hour urine collection will be conducted prior to the subsequent scheduled treatment (see Section 9.2.3.2.2).
- e Samples will be collected at Cycle 3, Cycle 5, Cycle 7, Cycle 9, and every 4 cycles thereafter while patient is on study treatment.

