Death or progression after more than one missed visit (after 3 months since last assessment)	Censored	Date of last radiologic assessment of measured lesions showing no progression prior to the missed visit

The date of first documented objective disease progression must be recorded on the CRF even if it occurs after the patient has started a new therapy.

Disease Control Rate (DCR): The proportion of patients in the analysis population who exhibit an SD or confirmed CR or PR relative to baseline during the study. Response is defined by RECIST 1.1 (Eisenhauer et al. 2009).

Change in Tumor Size (CTS): The change in tumor size from baseline to the measurement with the smallest tumor size during the study period. Change in tumor size will be assessed in each patient using radiographic imaging. The tumor size of target lesions will be determined as defined by RECIST 1.1 (Eisenhauer et al. 2009).

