6.16. Interim Analyses and Data Monitoring

An interim analysis will be performed after completion of Part A. Data will be reviewed on a cohort-by-cohort basis during the study until the MTD is determined. The purpose of these cohort-by-cohort reviews is to evaluate the safety data at each dose level and to determine if a DLT has been observed that would suggest MTD has been met or exceeded.

For Part B, both safety and efficacy data will be assessed. Interim analyses will be conducted after approximately 15 patients have completed 3 cycles in Parts B1,B2 and B4 (gastric, hepatocellular cancers and non-small cell lung cancer) and 6 cycles in Part B3 (renal cell cancer).

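### SAP 6.12 gives two PFS censoring rules that conflict after exactly one missed visit; the landmark PFS can move in either direction depending on which is programmed

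*SAP*

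**What the plan says.** The PFS paragraph of SAP 6.12 ends with a general rule: "If a patient has a missed visit prior to an event (progression or death), then the PFS time will be censored", with the censoring date set at the last evaluable assessment before the event. One missed visit is enough.

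Table 6.2, in the same section, has a narrower row: "Death or progression after more than one missed visit (after 3 months since last assessment"). The censoring date there is "Date of last radiologic assessment of measured lesions showing no progression prior to the missed visit". Objective progression that does not meet this row counts as an event. So does death in the row "Death before first objective PD assessment".

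The only link between the two is "Table 6.2 provides additional details". Nothing says which prevails, and neither place says that a missed visit means a missed tumor assessment.

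Protocol Attachment 1 schedules scans "Every 6 weeks after initiation of study treatment; after Cycle 9 every 2-4 cycles as clinically indicated", with a window of 7 days either side. SAP 6.12 names no estimator for PFS; Kaplan-Meier appears only in the SAP reference list.

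**The concern.** Two programmers following 6.12 could code the same patient in opposite ways. Take a clean week-6 scan, a missed week-12 scan and progression on the week-18 scan. The table gives an event at week 18; the text gives censoring at week 6. Or take a missed week-6 scan and death at week 9. The first table row gives an event; the text censors at baseline.

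PFS at a landmark is used for a decision. SAP 5.2 and Protocol 8.1.1 allow disease control, judged against the landmarks in Protocol Table JTBF.2, as an alternative ground for enlarging a cohort from about 15 to about 45 patients. In an open-label study the choice between two conflicting sentences should not be left until the data are visible.

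**Working it through.** **Inputs from the documents.** Scans every 42 days, within 7 days either side, up to Cycle 9. Median PFS of 2.1 months (gastric), 4 (HCC), 7.1 (RCC) and 3 (NSCLC). Landmarks at 12 weeks, 4, 7.1 and 3 months, that is days 84, 122, 216 and 91. The documents give no missed-scan rate, so 5%, 10% and 20% are assumed.

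**The plan's own figure.** 2.1 months is 9.13 weeks. Exponential PFS at 12 weeks is exp(-ln 2 × 12 / 9.13) = 40.2%, against the stated 40%. The other three landmarks are the medians, so 50%. The documents give no figure for the effect of either censoring rule.

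**Does the conflict arise on the planned schedule?** One missed scan after a clean scan leaves 2 × 42 = 84 days, which is under 3 months and only one miss. The table counts the event and the text censors it. Two misses leave 3 × 42 = 126 days, and both rules censor.

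**Do the table row's two conditions agree?** Not always.
- One miss plus window drift can reach 84 + 14 = 98 days.
- A baseline scan "may be from prior to consent if taken within 28 days of Day 1, Cycle 1" can lie 28 + 84 = 112 days before week 12 with one scan missed.
- After Cycle 9 (week 36) the interval is 56-112 days, so one miss leaves 112-224 days. This last problem falls after every landmark (the longest, 7.1 months, is about week 31) and affects only later PFS.

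**Which way does the landmark move?** Take 15 gastric patients: 4 progress at week 6, 4 at week 12, 3 at week 18, 3 are censored at week 24, and one patient is switched between the rules.
- Misses week 6, progresses at week 12. Table: 11/15 × 6/11 = 40.0%. Text (censored at baseline): 10/14 × 6/10 = 42.9%. Text is higher, because a failure before the landmark is removed.
- Misses week 12, progresses at week 18. Table: 11/15 × 7/11 = 46.7%. Text (censored at week 6): 11/15 × 6/10 = 44.0%. Text is lower, because a patient event-free at the landmark leaves the risk set early.

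**Size under Kaplan-Meier.** Simulation with 300,000 patients per setting: exponential PFS at the medians above, each scan uniform within its window, scans missed independently, progression events only, follow-up past the landmark. The text rule censors after one or more misses just before the event. The table rule needs two or more misses and more than 91 days. Landmark PFS in %, table / text:

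| Cohort and reading day | 5% missed | 10% missed | 20% missed | Text minus table |
|---|---|---|---|---|
| RCC, day 216 | 52.2 / 54.2 | 52.8 / 56.7 | 54.9 / 62.2 | +2.0, +3.9, +7.3 |
| HCC, day 122 | 59.7 / 60.5 | 60.2 / 62.0 | 61.8 / 65.5 | +0.8, +1.8, +3.7 |
| NSCLC, day 91 | 53.8 / 54.3 | 54.8 / 55.9 | 56.1 / 58.9 | +0.5, +1.1, +2.8 |
| Gastric, day 84 | 53.2 / 52.6 | 54.1 / 53.3 | 56.3 / 55.2 | -0.6, -0.8, -1.1 |
| Gastric, day 91 | 41.2 / 41.3 | 41.9 / 42.3 | 43.4 / 45.1 | +0.1, +0.4, +1.7 |

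Repeating the simulation moves the differences by 0.1 to 0.2 point. Gastric changes sign because day 84 is the middle of the week-12 scan window. About half of those scans fall later, so their progressions count as after the landmark. By day 91 the window has closed.

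**Single cohorts of 15** (10% missed, window applied). Text higher / lower / same: gastric 26/48/26%, HCC 41/23/35%, RCC 62/8/31%, NSCLC 42/31/27%.

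**Crude proportion of all treated patients known event-free.** For each patient the text rule's time is never later than the table's, and a patient censored before the landmark is not known event-free. The text rule can therefore never be higher. At 10% missed: gastric 54.2 (table) against 47.4 (text), NSCLC 53.8 against 48.9.

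**The case against.** The strongest counter-argument is that little depends on this. Analyses are descriptive (SAP 6.1), ORR is the co-primary measure and is untouched, and the landmark route to expansion is discretionary. That stands, and it limits the severity. It does not remove the contradiction, which is in current SAP text and cheap to resolve.

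A second argument is that the table merely elaborates the text. It cannot: for one missed visit the two give opposite outcomes.

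A reader might go further and infer that, because the text rule censors more failures, it must inflate landmark PFS. The first half is right. With scans exactly on schedule, the text censors 4.8%, 9.4% and 17.8% of gastric events seen by the landmark at 5%, 10% and 20% missed, against none under the table. For RCC it censors 7.8%, 15.2% and 29.1%, against 0.4%, 1.7% and 6.2%. The second half does not follow. Censoring is back-dated to the last scan, so it also removes patients who were event-free at the landmark. Simulating scans exactly every 42 days makes the text rule look uniformly higher (gastric 42.9 against 44.2 at 10% missed), but the protocol allows 7 days either side, and the day-84 gastric result then reverses.

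Missed scans may also be related to progression. If a miss is three times as likely at the first scan after progression, the RCC gap at 10% base missingness widens to 55.3 (table) against 63.7 (text). Gastric at day 84 is still lower under the text at 10% (60.2 against 59.2), and becomes higher at 20% (67.6 against 70.2).

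**Conclusion.** The conflict is real and certain from the wording: an event after exactly one missed visit is censored by the text of SAP 6.12 and counted by Table 6.2, with no precedence stated. The text rule censors more events, but the sign of its effect on landmark PFS is not fixed.

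Under Kaplan-Meier, the 7-day window and 5-20% of scans missed at random, the text rule is higher by about 2-7 points for RCC, about 1-4 for HCC and about 0.4-2.8 for NSCLC at day 91. For gastric it is about 0.5-1 point lower at week 12 and about 0-2 higher at day 91. These sizes rest on the assumed missed-scan rate, exponential PFS and an estimator that 6.12 does not name. Making 20% of events deaths does not change which cohorts move up or down.

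No probability of expanding a cohort is claimed, because the interims come before all patients reach the landmark. SAP 6.16 sets "6 cycles in Part B3 (renal cell cancer"), that is 168 days against 216; for HCC, 3 cycles are 84 days against 122. This should be corrected, but it does not threaten the study's main conclusions.

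**What to change.** In SAP 6.12:
- Delete the sentence on a missed visit and keep one rule based on Table 6.2.
- Define a missed visit as a missed scheduled tumor assessment.
- Replace the 3-month condition: censor only after two or more consecutive missed scheduled assessments, counted on the scan interval in force, at the last adequate progression-free scan before the gap.
- State which table row applies to a death after two missed scans with no post-baseline scan, since the first and last rows both fit.
- Name Kaplan-Meier as the landmark PFS estimator. Patients whose follow-up has not reached the landmark stay censored and are not counted as failures. Stating the reading day as well would settle the gastric case.
- Add a sensitivity analysis counting every observed progression and death as an event on the date observed, with a note that late detection after a missed scan makes it run high at short landmarks.

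The cost is SAP wording and one extra run. No visit, scan or treatment changes. The landmark estimate may move up or down compared with the text rule.
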